18.13. Fatigue Severity Scale (FSS)

#### Fatigue Severity Scale (FSS) of Sleep Disorders

The Fatigue Severity Scale (FSS) is a method of evaluating the impact of fatigue on you. The FSS is a short questionnaire that requires you to rate your level of fatigue.

The FSS questionnaire contains nine statements that rate the severity of your fatigue symptoms. Read each statement and circle a number from 1 to 7, based on how accurately it reflects your condition during the past week and the extent to which you agree or disagree that the statement applies to you.

- A low value (e.g., 1) indicates strong disagreement with the statement, whereas a high value (e.g., 7) indicates strong agreement.
- It is important that you circle a number (1 to 7) for every question.

FSS Questionnaire								
During the past week, I have found that:	Disagree <> Agree							
My motivation is lower when I am fatigued.	1	2	3	4	5	6	7	
Exercise brings on my fatigue.	1	2	3	4	5	6	7	
I am easily fatigued.	1	2	3	4	5	6	7	
Fatigue interferes with my physical functioning.	1	2	3	4	5	6	7	
Fatigue causes frequent problems for me.	1	2	3	4	5	6	7	
My fatigue prevents sustained physical functioning.	1	2	3	4	5	6	7	
Fatigue interferes with carrying out certain duties and responsibilities.	1	2	3	4	5	6	7	
Fatigue is among my three most disabling symptoms.	1	2	3	4	5	6	7	
Fatigue interferes with my work, family, or social life.	1	2	3	4	5	6	7	
			Tot	al Sc	ore:			

Copyright Lauren B. Krupps. Reproduced with permission of the author.

Amendment 04, Final Version 1.0
Protocol No.: BB-2001-201b 07/Nov/2018
EudraCT No.: 2017-000877-35 Page 141 / 142

#### 18.14.Berlin Questionnaire (BQ)

1	Complete the following: height age weight sex	7 How often do you feel tired or fatigued after your sleep?  ☐ nearly every day ☐ 3-4 times a week ☐ 1-2 times a week
3 2	Do you snore? yes no don't know	☐ 1-2 times a month ☐ never or nearly never
22	W. C.	8 During your wake time, do you feel tired,
	you snore:	fatigued or not up to par?
3		nearly every day
	slightly louder than breathing	☐ 3-4 times a week
	as loud as talking	☐ 1-2 times a week
	☐ louder than talking	☐ 1-2 times a month
	very loud, can be heard in adjacent rooms	☐ never or nearly never
		9 Have you ever nodded off or fallen
4	How often do you snore?	asleep while driving a vehicle?
	nearly every day	□ yes
	☐ 3-4 times a week	□ no
	☐ 1-2 times a week	
	☐ 1-2 times a month	If yes, how often does it occur?
	☐ never or nearly never	☐ nearly every day
		☐ 3-4 times a week
5	Has your snoring ever bothered	☐ 1-2 times a week
	other people?	☐ 1-2 times a month
	□ yes	☐ never or nearly never
	□ no	
6	Has anyone noticed that you quit	m 10 Do you have high blood pressure?
	breathing during your sleep?	w 10 Do you have high blood pressure?  yes □ no □ don't know
	nearly every day	g □ no
	☐ 3-4 times a week	₩ □ don't know
	☐ 1-2 times a week	3
	☐ 1-2 times a month	BMI =
	☐ nearly or nearly never	

#### Berlin Questionnaire Scoring:

Scoring Questions: Any answer within box outline is a positive response

Scoring Categories: Category 1 is positive with 2 or more positive responses to questions 2-6

Category 2 is positive with 2 or more positive responses to questions 7-9. Category 3 is positive with 1 or more positive response and/or a BMI >30

Final Results: 2 or more positive categories indicates a high risk of obstructive sleep apnea

Netzer, N. C., R. A. Stoohs, et al. (1999). "Using the Berlin Questionnaire to identify patients at risk for the sleep apnea syndrome." Ann Intern Med 131(7): 485-491 (41).

Amendment 04, Final Version 1.0
Protocol No.: BB-2001-201b
EudraCT No.: 2017-000877-35
Amendment 04, Final Version 1.0
07/Nov/2018
Page 142 / 142

#### 18.15. Schedule of Assessments

VISITS Week	Screening period (W-4)	Baseline period (W-1)	Randomisation Visit 1	Treatment Visit 2 (W2)		Treatment Visit 3 or Early Term (W6)	FUP (1)
Study days (referred to D1 [Day of first administration]	D-28 to D-8	D-7 to D-2	D-1	D14 (± 2)	D35	D42 (± 3)	+D28 (± 2)
(allowed deviation days in brackets)							
Informed consent	X						
Inclusion and exclusion criteria	X	$X^{(3)}$	X 				
Demographics	X						
Medical history and previous medication	$X^{(4)}$	X					
Concurrent Medical Condition	X						
Physical examination	X					X	
Vital signs (including heart rate and blood pressure)	X			X		X	X
Pregnancy test	X		X 			X	
Laboratory tests	X	X 				X	
Pharmacogenomic blood sample	X 						
Electrocardiogram	X					X	
Eye examination	X					X 	
Epworth Sleepiness Scale (ESS)	X		X	X		X	
Scales for Outcome in Parkinson's Disease Sleep (SCOPA-Sleep)			X	X		X	
Parkinson's Disease Sleep Scale (PDSS-2)			X	X		X	
Fatigue Severity Scale (FSS)	X					X	
Berlin Questionnaire (BQ)	X						
Unified Parkinson's Disease Rating Scale (UPDRS Part III) 			X	X		X	
Cognitive Impairment (Montreal Cognitive Assessment – MoCA	X					X	
Hamilton Rating Scale for Depression (HAM-D) $^{(10)}$	X			X		X	X
Columbia-Suicide Severity Rating Scale (C-SSRS) (10)	X			X		X	X
Brief Psychiatric Rating Scale positive subscale (BPRS+) 	X			X		X	X
Maintenance of Wakefulness Test (MWT) 		X				X	
Polysomnography 		X				X	
Free living activity (GENEActiv ®)(2)		X	X		X	X	
Randomisation			X				
Treatment intake 				X	X	X	
Adverse Events		X	X	X	X	X	X
Concomitant medication		X	X	X	X	X	

- (1)All subjects will perform a safety follow-up visit 28 days after last study visit performed.
  - Additional unscheduled visits may be arranged in case of eye examination, ECG, or adverse event findings.
- (2) GENEActiv® to be worn for 7 days continuously on the non-dominant hand day -7 to day -1 at baseline and before the last dose, day 35 to day 42.
- (3) Inclusion / Exclusion criteria to be reconfirmed before randomisation
- (4) Prohibited medical history will be assessed 4 weeks before Screening D-28
- (5) Dipstick pregnancy test to be completed before randomisation
- (6) If there are more than 14 days between screening and baseline
- (7) Pharmacogenomic blood sample to be obtained in subjects who specifically consented for this exploratory analysis.
- (8) The eye examination should be performed after the last treatment on Day 42 and before the follow up safety call.
- (9) Subjects will be instructed to have already taken their normally scheduled dose of anti-parkinsonian medication and their IMP prior to arriving at the study site in order to have their UPDRS Part III evaluated in ON (within approximately 1 to 3 hours after taking their levodopa dose). UPDRS in OFF will not be evaluated.
  - It is recommended that all assessment (s) establishing eligibility for the study to be performed first.
- (10) Any positive finding on the HAM-D, C-SSRS, or BPRS+ scales during the study will be referred to a trained mental health professional to be followed.
- (11) MWT and Polysomnography will be performed on a minimum of 50% of subjects (all recruited in sites with sleep units available)
- (12) Treatment will be taken from Day 1 to Day 42, both inclusive.

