### 7.0 Investigational Plan

# 7.1. Overall Study Design and Plan: Description

This phase 2b study is designed as multicentre, multinational, randomized, double blind, parallel group and placebo controlled with three doses of Bavisant (0.5, 1, and 3 mg/d) in subjects with excessive daytime sleepiness with Parkinson's disease. This study will involve approximately 230 subjects from around 48 sites globally.

Eligible subjects will be randomly allocated at a ratio of 1:1:1:1 to either Bavisant (at doses of 0.5, 1, and 3 mg/d) or placebo.

After signing the study informed consent, subjects meeting the UK PDS Brain Banks Diagnostic Criteria for Parkinson's disease (see details in Appendix 18.2) will enter a screening period (lasting up to 3 weeks) followed by a baseline period (lasting up to 1 week). Key inclusion / exclusion criteria will be verified to determine subject eligibility at the screening, baseline periods and prior to randomisation, including the suicide risk assessment following the FDA Guidance for Industry on Suicidal Ideation and Behavior.

[figure not shown]
There is a 6 weeks treatment period, starting on Day 1, followed by a safety follow-up at least 4 weeks after completion of the treatment period. Additional unscheduled visits may be required based on the investigators' judgement at the end of study visit or at the safety follow-up. For early termination, all the assessments of the treatment week 6 visit should be performed, if possible, including the safety follow-up 4 weeks after the last IMP administration.

A schematic of the study design is included in Figure 1 and the schedule of assessments is listed in Appendix 18.15.

Protocol No.: BB-2001-201b 07/Nov/2018 EudraCT No.: 2017-000877-35 Page 39 / 142

Figure 1. Study figure

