# 8.4.1.15.1 Unified Parkinson's Disease Rating Scale (UPDRS Part III)

The Unified Parkinson's Disease Rating Scale Part III (UPDRS Part III) is one of the secondary efficacy endpoints and will be assessed at baseline (day -1), visit 2 (day 14), and visit 3 (day 42) or early termination. Patients will be instructed to have already taken their normally scheduled dose of anti-parkinsonian medication and their IMP prior to arriving at the study site in order to have their UPDRS Part III evaluated in ON (within approximately 1 to 3 hours after taking their levodopa dose). UPDRS in OFF will not be evaluated.

The UPDRS is the most widely used clinical rating scale for PD. The UPDRS was originally developed in 1987, and a new version was sponsored in 2001 by the Movement Disorder Society in order to retain the strengths of the original scale, but resolving identified problems and especially incorporating a number of clinically pertinent PD-related problems poorly captured in the original version. The original four component (Parts I-IV) design was retained, but the focus of each part was changed. Part I concerns "non-motor experiences of daily living", Part II concerns "motor experiences of daily living", Part III is retained as the "motor examination", and Part IV concerns "motor complications". Rater involvement time for administering the UPDRS is estimated to require less than 15 minutes for Part III. Each question is anchored with five responses that are linked to commonly accepted clinical terms of 0 (normal), 1 (slight), 2 (mild), 3 (moderate), and 4 (severe). Part III contains 33 scores based on 18 items, several with right, left or other body distribution scores. An UPDRS Part III sample questionnaire has been included in Appendix 18.8.

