## 8.4.1.15.9 Free Living Activity

Approximately half (50%) of subjects participating in the clinical study will be offered an opportunity to take part in the assessment of free living activity as an exploratoty assessment. A wrist-worn actigraphy device (GENEActiv®) will be provided to these subjects and they will be required to wear the actigraphy device on their non-dominant wrist for 7 consecutive days during the baseline period (day -7 to day -1) and 7 consecutive days **before** the last dose on visit 3 (day 35 to day 42).

The wrist-worn actigraphy device (GENEActiv®) is a tri-axial accelerometer which provides an objective measure of physical activity levels. A study manual with instructions will be provided to both the investigators and the subjects.

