# Treatment Visit 3 (Day 42 ±3)

This visit will be performed 6 weeks after the 1st treatment administration (Day 1). The following examinations/procedures will be performed:

- Physical examination
- Vital signs
- Laboratory (haematology, biochemistry), serum pregnancy test (for women of childbearing potential)
- Electrocardiogram, heart rate, blood pressure
- Assessment of sleepiness scales: ESS, SCOPA-Sleep, PDSS-2
- Maintenance of Wakefulness Test (MWT)

Protocol No.: BB-2001-201b EudraCT No.: 2017-000877-35 Amendment 04, Final Version 1.0 07/Nov/2018 Page 61 / 142

- Polysomnography
- Cognitive assessment (MoCA)
- Columbia-Suicide Severity Rating Scale (C-SSRS)
- Fatigue assessment (FSS)
- Other scales: UPDRS Part III, HAM-D and BPRS+
- Wrist-worn actigraphy assessment 7 days continuously **before** last dose (day 35 to day 42).
- Wrist-worn actigraphy device return
- Drug return and accountability
- Recording of adverse events
- Recording of concomitant medication
- Eye examination (should be performed after the last treatment on Day 42 and before the follow up safety call)

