### **8.6.2** Identity of Investigational Product(s)

# **Experimental treatment:**

Product Name: Bavisant tablets 0.5/1/3 mg

Drug substance: Bavisant dihydrochloride monohydrate

Pharmaceutical Form: Tablets containing Bavisant dihydrochloride monohydrate equivalent

to 0.5/1/3 mg of Bavisant

Administration route: Oral use

Dosage: Once daily administration

Manufacturer: Nuvisan GmbH, [name]

Control treatment:

Control substance: Placebo Pharmaceutical Form: Tablets

Amendment 04, Final Version 1.0
Protocol No.: BB-2001-201b
EudraCT No.: 2017-000877-35
Page 66 / 142

Administration route: Oral use

Dosage: Once daily administration

Manufacturer: Nuvisan GmbH, [name]

The IMP will be supplied in wallet cards. The IMP will be identifiable by a unique identification number. The wallet cards will contain a surplus of tablets to cover the treatment period and visit windows. The IMP should be stored at 25°C; excursions permitted to 15°C to 30°C.

Each card of investigational medication will be labelled with pertinent study information and country-specific regulatory caution statements in country-specific language(s).

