### 8.6.3 Dosages and Regimen

Each subject who qualifies for the study will receive wallet cards containing tablets of double-blind study medication. Subjects will receive 1 wallet card of their assigned treatment at Visit 1 (for 2 weeks treatment period) and 2 wallet cards at Visit 2 (for 4 weeks treatment period).

Subjects will be instructed to take 1 tablet orally per day at the same time in the morning, with or without food. The first dose is to be taken the day after randomisation when study medication has been dispensed to the subject.

The investigator or designee must instruct the subject to bring each of their study medication containers (wallet cards) to each clinic visit, regardless of whether the study medication cards are empty.

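### The fixed Day 42 end of dosing cannot be followed together with the Day 39–45 window for Visit 3 and the instruction to take IMP before the UPDRS Part III rating, and the SAP has no check on time since last dose

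*Protocol*

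**What the plan says.** Section 7.1 of the protocol states: "There is a 6 weeks treatment period, starting on Day 1". Section 8.6.3 fixes the time of day: "Subjects will be instructed to take 1 tablet orally per day at the same time in the morning, with or without food". The end of dosing is then described in several ways.

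- **Fixed day.** Footnote (12) of section 18.15: "Treatment will be taken from Day 1 to Day 42, both inclusive". Footnote (8) and the Visit 3 list in section 8.4.2 also place the last treatment on Day 42, when they time the eye examination.
- **Visit window.** Sections 8.4.2 and 18.15 allow Visit 3 at Day 42 ±3.
- **Dose before the visit.** Footnote (9) tells subjects to have taken "their IMP prior to arriving at the study site in order to have their UPDRS Part III evaluated in ON". Section 8.4.1.15.1 gives the same instruction and names Visit 3 among the UPDRS III visits.
- **Last dose at the visit.** Section 8.4.1.15.9 has the actigraph worn for seven days before "the last dose on visit 3 (day 35 to day 42"), which treats Visit 3 and Day 42 as the same day. The Early Termination text in section 8.4.2 does likewise.
- **Supply.** Section 8.6.2: "The wallet cards will contain a surplus of tablets to cover the treatment period and visit windows".
- **Drug return.** Sections 8.4.2 and 8.6.8 have unused drug returned at Visit 3.

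SAP section 4.1 leaves nominal Visit 3 records where they are. It lets early-termination or unscheduled values from Days 22 to 45 fill a missing Visit 3. Neither rule considers when the last dose was taken.

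**The concern.** A late Visit 3 can be handled in two ways, and the protocol supports both. One site may stop drug after Day 42 and assess the subject without it. Another may continue, using the surplus tablets, and assess the subject a few hours after a dose. Both results enter the analysis as week 6.

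This matters most where Visit 3 is the only scheduled on-treatment measurement: ECG with QTc, laboratory tests, MWT and polysomnography. UPDRS III and blood pressure are also taken at Visit 2, but their week-6 values are open to the same mixing. If drug effect fades over one to three days, a mixed week-6 value could blur comparisons between doses and placebo, or make an on-treatment ECG finding look smaller than it is.

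**Working it through.** The inputs are days taken from the protocol. No sample size, power or alpha enters.

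**The plan's own figure.** Dosing days = 42 − 1 + 1 = 42, and 42 / 7 = 6.0 weeks. Footnote (12) therefore agrees with the six-week period in section 7.1.

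**Visit window.** 42 − 3 = 39 and 42 + 3 = 45, so there are 45 − 39 + 1 = 7 permitted days.

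**Gap under footnote (12)** = visit day − 42:

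| Visit 3 on | Days since Day 42 dose | Can the instructions be followed together? |
|---|---|---|
| Days 39–41 | not yet reached | No: drug is returned at the visit, but dosing should run to Day 42 |
| Day 42 | 0 | Yes |
| Day 43 | 1 | No: footnote (12) bars a dose that morning, footnote (9) requires it for UPDRS III |
| Day 44 | 2 | No, same reason |
| Day 45 | 3 | No, same reason |

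Three of the seven days (3 / 7 = 43%) fall after the last dosing day. This is a share of calendar days in the window. The documents give no distribution of visit days, so it is not a share of subjects.

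**Which assessments are tied to a dose.** The instruction to take "and their IMP prior to arriving at the study site" stands in the UPDRS Part III section, and footnote (9) hangs on the UPDRS III row. No equivalent is written for ESS, SCOPA-Sleep, PDSS-2, MWT, polysomnography, ECG, laboratory tests or blood pressure. On Days 43–45 the direct contradiction is therefore for UPDRS III. The other assessments follow whatever the subject did that morning, so under footnote (12) they also come 1 to 3 days after the last dose, but no rule on prior dosing is broken.

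**A side effect on compliance.** Section 8.6.10 divides tablets used by days between visits. Take a fully adherent subject with Visit 2 on Day 14 who stops on Day 42. Tablets used between the visits are 42 − 14 = 28. With Visit 3 on Day 43, 44 or 45 the formula gives 28/29 = 96.6%, 28/30 = 93.3% or 28/31 = 90.3%, although no dose was missed.

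**The case against.** The best reply is that Day 42 is only the nominal day of Visit 3 and that dosing is meant to run through the visit. Several places support this. The actigraphy text puts the last dose at Visit 3. The treatment-intake row of section 18.15 is marked in the Visit 3 column, which carries the ±3 window. Surplus tablets are supplied for the windows. SAP section 13.5 defines exposure as last dose date minus first dose date and has a category above 6 weeks. A last dose on Day 42 gives 42 − 1 = 41 days, and exceeding 42 days needs a last dose on Day 44 (44 − 1 = 43) or later, so the SAP allows for dosing past Day 42. This reading is plausible, and it means that a late visit need not be an off-drug visit. It does not cancel footnote (12), which states both end days as included, or the two other places that put the last treatment on Day 42. A site can reasonably follow either.

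It may also be said that the blind data review in SAP section 6 considers the timing of visits. A visit on Days 43–45 is within the window, however, so nothing in that list would single it out.

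Three stronger readings are tempting, and the documents do not support them. First, a reader might infer that all Visit 3 assessments require IMP that morning; the rule covers UPDRS III only. Second, a reader might infer that the primary endpoint or the QTc result is biased by a known amount. No half-life, off-drug effect or visit-day distribution is given, and section 7.2 describes the ESS recall as a few weeks to a few months. Third, a reader might infer that the MWT is bound to fall after the last dose because it follows the polysomnography night. Section 8.4.1.15.7 says the MWT usually follows a night's sleep, but no text puts that night on Day 42.

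**Conclusion.** The contradiction is in the current protocol and should be corrected. Dosing to a fixed Day 42, a Visit 3 window of Days 39–45 and IMP before the UPDRS III rating cannot all be met on Days 43–45. On Days 39–41, drug return at the visit conflicts with dosing to Day 42. If footnote (12) is applied literally, late visits are 1 to 3 days after the last dose. If sites differ in practice, week-6 values could mix drug states without the SAP revealing it.

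The day counts are certain. Any harm to the results is possible but not quantifiable from these documents. It depends on how many visits fall after Day 42, which text the sites follow and how fast the effect fades. UPDRS III, MWT, polysomnography, ECG/QTc and blood pressure are the more exposed measures; the ESS is little exposed.

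**What to change.** **Protocol.** Reconcile sections 8.4.1.15.1, 8.4.1.15.9, 8.4.2 (Visit 3 and Early Termination), 8.6.2 and 18.15 (intake row and footnotes 8, 9 and 12) so that they agree and can be followed on every day from 39 to 45. Which rule applies is for the sponsor to decide; none is proposed here.

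**SAP.** Section 13.5 already needs the last dose date. Use it to derive the days from last dose to each Visit 3 assessment, and flag values taken more than one day after. Repeat the UPDRS III, MWT, polysomnography and ECG/QTc summaries without the flagged values. Tabulate the gap in days by arm as well, because a Day 43 visit after a Day 42 dose is exactly one day and would not be flagged. Read the repeat as a sensitivity check, since it excludes values on a post-randomisation feature. A date alone cannot show whether a same-day dose came before the rating.

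**Cost.** A wording amendment and one extra SAP output. No added visits or subjects.

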1 INTRODUCTION

The objective of this statistical analysis plan (SAP) is to specify the statistical analysis in more detail than stated in the protocol for the trial. The statistical analysis plan does not change the analysis described in the protocol, but it should be precise enough to serve as a guideline for statistical programming and creation of tables. The statistical analysis plan (SAP) will ensure the credibility of the study findings by specifying the statistical approaches to the analysis of the double-blind data prior to database lock.

This Statistical Analysis Plan was developed based on the International Conference on Harmonization (ICH) E3 and E9 Guidelines and with reference the valid protocol (final version v1.0 amendment 03, dated 23Aug2017). Deviations from the planned methods should also be summarized in Section 14 of this SAP. Any deviations during the analysis and reporting process from the current statistical analysis plan will be described and justified in the final report

2 RESPONSIBILITIES

The statistical analysis, interpretation and reporting will be the responsibility of the assigned project biostatistician.

All analyses and reporting will be subject to a quality check process.

3 STUDY OBJECTIVES

3.1 Primary Objectives

To assess the efficacy of Bavisant compared to placebo after a 6-week treatment period on the excessive daytime sleepiness in Parkinson's disease.

3.2 Secondary objectives

To assess the efficacy and safety assessment of Bavisant compared to placebo after 2 weeks and 6 weeks of treatment. The efficacy assessment will include excessive daytime sleepiness, motor control, and depression.

